3.3.4.3. Pre- Hospital Discharge

The following evaluations will take place prior to the subject's discharge from the hospital:

- CT without contrast and CTA (contrast enhanced CT) covering the length of the lesion, which may include scans of the chest, abdomen and pelvis; MRA may be used at the investigator's discretion.
 - NOTE: If the discharge occurs within the one-month follow-up window, only one set of CT/CTA images is needed.

- Vital signs [heart rate, blood pressure, respiratory status, pulse evaluation (Bilateral Radial, Dorsalis, and/or Tibial arteries where applicable.)]
- Adverse event and technical observations, evaluations, and treatments should be documented in the appropriate CRFs.
- All subjects with a history of stroke or have any post-procedural neurological deficit(s) will undergo neurological examination. A diffusion weighted MRI of the head will also be performed on these patients when clinically indicated.

3.3.4.4. Follow-up Examinations

Follow-up evaluations will be scheduled for 1 month (t 14 days), 6 months (\pm 60 days), 12 months (\pm 90 days) and annually thereafter to 5 years post implant (\pm 16 weeks).

The following tests and procedures will be included at each of these visits:

- Vital signs [heart rate, blood pressure, respiratory status, and pulse evaluation (Bilateral right Dorsalis, and/or Tibial artery where applicable)]
- Chest x-ray (2- or 4-view, as per standard of care).
- CT without contrast and CTA (contrast enhanced CT) covering the length of the lesion, which may include scans of the chest, abdomen and pelvis; MRA may be used at the investigator's discretion.
- Adverse event and technical observations, evaluations, and treatments should be documented in the appropriate CRFs.
- Echocardiogram at the 1 month, 12 month, and yearly visits.
- KCCQ questionnaire.

The following tests may also be ordered at the discretion of the investigator:

- Echocardiogram (after the 1 month, 12 months, and yearly follow-up)
- Diffusion weighted MRI of the head
- Neurocognitive evaluation using the NIH stroke scale
- Neuropsychological evaluation.

Per standard of care, the patients will undergo lifelong follow-up after they have completed the study. This follow-up regimen is consistent with current recommendations for patients with thoracic aortic dissections. This longitudinal imaging regimen with 3-dimensional center-of-flow reconstruction using the M2S (Lebanon, NH) or similar software will allow for morphologic changes of the aorta and structural changes of the stent graft in the long-term follow-up.

The data collection schedule is summarized in Table 1.

Table 1: Study procedures and data collection requirements

Data	Screening/ Baseline	Procedure	Pre-Hospital Discharge	1 month FU +/- 14 days	6 Month FU +/- 60 days	12 Month FU +/- 90 days	2-5 Year FU +/- 16 weeks
Informed Consent	x						
Medical History	x						
Vital Signs, Pulse	x		x	x	x	x	x
KCCQ Questionnaire	x			x	x	x	x
Pregnancy test (if applicable)	x						
Laboratory Tests Serum Creatinine	x						
CT w/out contrast & CTA/MRA	x		x	x	x	x	x
Echocardiogram	x			x		x	x
Device & Procedure Information		x					
Angiogram		x					
Chest X-Ray				x	x	x	x
Adverse Event Assessment		x	x	x	x	x	x

3.3.4.5. Unscheduled Visits

If a patient has a visit specifically associated with the treated thoracic lesion and/or the Medtronic Thoracic Stent Graft System and this visit is not within any of the protocol specified study-related visit windows, data should be recorded as appropriate on the Unscheduled Follow-Up Form.

3.3.4.6. CT/CTA Scan

Images of the CT without contrast and CTA (contrast enhanced CT) covering the length of the lesion, which may include scans of the chest, abdomen and pelvis will be submitted for evaluation through 60 months of follow-up. Images at pre-procedure, pre-discharge, 1 month, 6 months, 12 months, 24 months, 36 months, 48 months and 60 months will be evaluated. In addition, any interim imaging done within one year of implantation should be evaluated if it relates to the performance of the implanted device. These data will be used for analysis of secondary observations at pre-discharge, 1 month, 6 months and 12 months. Site data will be used for reporting purposes at 24 months, 36 months, 48 months and 60 months, and submitted for central review.

The presence of the following endpoint related events would be assessed:

- Loss of stent graft patency
- FL diameter over the length of the stented segment
- TL diameter over the length of the stented segment
- Total aortic diameter
- FL thrombosis
- Changes in true and false lumen volumes over time
- Stent graft migration
- Presence and type of endoleaks
- Continuing or new false lumen (FL) perfusion

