Subject follow up, as outlined in Section 3.3.4.4 (Follow up Examinations), will involve experienced research staff that will be conducting study responsibility per the oversight of the PI. The imaging core lab will be used for patient safety review and measures.

Additional risk mitigation efforts are categorized below as general risk mitigation strategies and targeted risk mitigation efforts (i.e. those aimed at certain potential complications):

Table 3: Clinical Study Mitigation Strategies

Part Name	Function	Associated Failures	Functional Effect	Clinical Harm	Additional Actions Taken for Valiant Captivia PS-IDE Device and Ref. No ¹	Clinical Study Mitigation Strategies
Stent Graft	Stent graft can't be visualized	Markers Not Distinguishable Under Flouro	Inaccurate Delivery	Thrombus Formation	DV Report – 10036987DOC	For all events -Close patient follow-up for detection, treatment, and reporting of adverse events For Dissection progression aneurysm enlargement, rupture, and endoleaks -Completion angiogram will be performed to look for any evidence of blushing. If blushing is observed the stent may be ballooned or a cuff may be used for endoleaks and a covered stent graft may be used for endoleaks or if the original device fails -Scheduled follow-up imaging to monitor device and dissection/aneurysm -Implant additional devices (cuffs, stents) if the original device fails For embolism, lumen obstruction, vessel occlusion, or ischemia/organ failure -Pre-operative imaging for patient selection with appropriate anatomy
			Increased Procedure Time	Stroke	Sim Use Report – 10037136DOC DVT Protocol TP4370	
			Endoleak Type III (acute)	Limb Ischmeia	Stent Graft Expansion Integrity, QS116313	
			Occlusion	Conversion to Vascular Bypass	Radiopacity of Stent Graft Marker Bands, TM115688 Deployment Test, TM112037 In-vivo Evaluation TP3689	
				Surgical Conversion	PS274 Cadaver Study	
				Dissection		
				Extension of Dissection		
				Vessel Perforation		
				Radiation/Contrast Media/Anesthetic overexposure		
				Death		

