3. Unsuccessful repair or early endoleak, possibly leading to rupture of the aorta and death - ballooning of the end leaking landing zone may mitigate this risk. Addition of a larger stent graft at this location may reduce the endoleak as well. Alternatively, if the patient would need open conversion to fix any severe endoleak, the investigators would offer open repair immediately.
4. Propagation of dissection into the aortic root, possibly causing acute aortic regurgitation, or coronary dissection/occlusion, both leading to shock, conversion to surgery, or death - prompt diagnosis is paramount. This is facilitated by routine use of transesophageal echocardiogram. Immediate open surgical repair by an experienced team is key for a good outcome in this severe complication.
5. Delayed endoleak, possibly leading to rupture of the aneurysm and death; routine and close follow-up interval with various imaging techniques is key for detection of late endoleak. The repair options were discussed in #3.
6. Vessel rupture, possibly leading to shock, conversion to surgery, or death; immediate diagnosis and repair using endovascular or open techniques are key to a satisfactory outcome.
7. Migration of the device, possibly leading to rupture of the aorta, open surgery, or death — small migrations may be watched under close surveillance protocols. Other migrations may need additional stent grafting or open repair to mitigate the risk involved.
8. Blood loss, possibly leading to shock or death - this is usually promptly treated with appropriate blood product transfusion. Emergent surgery will ensure if necessary. Any injuries causing major bleeding will be addressed promptly by endovascular or open means.
9. Graft twisting or kinking, possibly leading to shock or death - most stent graft twisting and kinking warrant conservative therapy with close monitoring, while the hemodynamically significant issues will need open or endovascular options.
10. Infection, possibly leading to septicemia or death - the investigators and the OR team maintain a strict sterile field during the TEVAR procedure. Appropriate antibiotic prophylaxis is provided within an hour prior to skin incision.
11. Occlusion of blood flow to the spinal cord, possibly leading to temporary or permanent paraparesis or paraplegia - this is a rare complication for patients

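### Device-related interim imaging must be evaluated only in the first year after implant, so an endoleak, migration, occlusion or new false-lumen perfusion imaged and repaired between later annual scans may be missing from the 24 to 60 month imaging results

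*Combined protocol and SAP*

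**What the plan says.** Section 3.3.4.6 (CT/CTA Scan) first fixes the scheduled series: "Images at pre-procedure, pre-discharge, 1 month, 6 months, 12 months, 24 months, 36 months, 48 months and 60 months will be evaluated". It then adds unscheduled scans, with a time limit: "any interim imaging done within one year of implantation should be evaluated if it relates to the performance of the implanted device". Two sentences on use follow. The first is "These data will be used for analysis of secondary observations at pre-discharge, 1 month, 6 months and 12 months". The second is "Site data will be used for reporting purposes at 24 months, 36 months, 48 months and 60 months, and submitted for central review". The section ends with the events to be assessed on images, among them loss of patency, migration, endoleak and continuing or new false-lumen perfusion. That list has no one-year limit.

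Section 3.3.4.4 sets the visits after the first year as "annually thereafter to 5 years post implant", with a window of 16 weeks either side. The preceding visit is headed "12 Month FU +/- 90 days" in Table 1. The risk sections lean on late imaging. On delayed endoleak, Section 3.4.2.2 (item 5) says that "routine and close follow-up interval with various imaging techniques is key for detection of late endoleak". Section 3.4.2 adds: "The imaging core lab will be used for patient safety review and measures".

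Other sections also capture late events, and none of them stops at one year:

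- Section 3.3.4.5 has a form for unscheduled visits related to the lesion or device.
- Section 3.3.4.8 requires adverse events to be reported, and specifically requires endoleaks arising after implant, and procedures to correct them, to be entered on a case report form.
- Section 3.3.5.1 makes re-intervention and surgical conversion primary endpoints. It lists endoleak, migration and loss of patency as secondary endpoints without tying them to scheduled scans.

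**The concern.** After month 12 the scheduled scans are furthest apart. A scan prompted by symptoms or suspicion between two annual visits is then the one most likely to show a late device problem, yet the duty to evaluate such scans ends at one year. If the problem is treated before the next annual scan, the evaluated series moves from one acceptable image to another and the failure between them is not in it.

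What is at stake is the long-term description of device performance. The 24 to 60 month results for migration, patency and false-lumen perfusion could look better than the patients' course. The image that explains a late re-intervention could also go without evaluation in a study that relies on its core lab for safety review.

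**Working it through.** The plan states no figure that depends on the interim-imaging rule, so there is nothing to reproduce. The check has four parts: what the rule covers, how far apart late scans can be, which events have another route into the data, and how much one event weighs.

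**1. What the rule covers.** Section 3.3.4.6 says at its start that CT/CTA images are submitted for evaluation through 60 months. It then names the scheduled images, and then adds interim images from the first year. If the opening statement already covered interim scans at any time, the added sentence and its limit would do no work. The natural reading is that interim scans in years 2 to 5 carry no evaluation requirement. That is four of the five years of follow-up.

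**2. Spacing of late scans.** Inputs from Section 3.3.4.4 and Table 1: nominal days 365, 730, 1095, 1460 and 1825; windows of 90 days at month 12 and 16 weeks (112 days) at each later visit.

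- Longest separation = (next day + its window) − (previous day − its window).
  - Months 12 to 24: (730 + 112) − (365 − 90) = 567 days, or 81 weeks.
  - Each later pair: 365 + 112 + 112 = 589 days. In weeks, 52 + 16 + 16 = 84.
- Time between windows = (next day − its window) − (previous day + its window).
  - Months 12 to 24: (730 − 112) − (365 + 90) = 163 days.
  - Each of the three later pairs: 365 − 112 − 112 = 141 days.
  - Total: 163 + 3 × 141 = 586 of 1,460 days, or 40% of months 12 to 60.

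**3. Other routes into the data after year 1.**

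| Event | Route with no one-year limit | Stated evaluation of an interim image |
|---|---|---|
| Re-intervention, conversion | Primary endpoint, Section 3.3.5.1 | None |
| Endoleak and its repair | Specific case report form rule, Section 3.3.4.8 | None |
| Migration, occlusion | General adverse event, technical observation or unscheduled-visit recording only; listed as secondary endpoints | None |
| New false-lumen perfusion | General recording only; listed as an imaging event in Section 3.3.4.6 | None |

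Section 3.3.5.3 summarises secondary endpoints by known values and percentages. It does not say whether an event found and treated between scheduled scans counts at the next time point.

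**4. Weight of one event.** With the planned 20 patients, 1/20 = 5 percentage points. If fewer patients have a known value at a late visit, the shift is larger: 1/n for n patients.

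The documents give no late-failure rate. Purely as an assumption, take a constant annual rate r over years 2 to 5, no death or dropout, and failures spread evenly in time. Expected failures are 20 × [1 − (1 − r)^4], and the part arising between windows is that number × 586/1,460.

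| Assumed r | Expected failures in 20 | Arising between windows |
|---|---|---|
| 2% | 1.6 | 0.6 |
| 5% | 3.7 | 1.5 |
| 10% | 6.9 | 2.8 |

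The last column is not an estimate of omissions. An omission also requires that the failure be imaged and repaired before the next scheduled scan and not be counted from a case report form.

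**The case against.** The strongest reply is that the events are captured even if the image is not evaluated. A reader might infer that a late failure repaired between annual scans never reaches the imaging endpoints. The documents do not support that. Section 3.3.5.1 does not restrict endoleak or migration to scheduled or centrally read scans. Section 3.3.4.8 requires a late endoleak, its type and possible cause, and its repair to be recorded. The repair itself can count as a primary re-intervention. This stands, and it limits the point to evaluation of the interim image and to events without a specific reporting rule.

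A second reply is that Section 3.3.4.6 adds a duty in year 1 and forbids nothing later. This also stands in part: the core lab is not barred from reading a late interim scan. But a limit written into the rule leaves no requirement beyond it.

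A third reply is that the one-year limit matches the plan's own boundary, since image data feed the secondary analysis only to month 12 and site data are reported afterwards. That explains the limit but does not settle the matter. The same section evaluates the scheduled late images and sends late data for central review, and the synopsis lists centralised measurements annually to five years. Which source decides a late event is left open.

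Two supports for a larger claim should not be used. The background cites a 10-patient series with 2 late interventions for endoleak. Those leaks were persisting ones, mean follow-up was 10 months, and nothing places them after year 1. Nor do the documents show a core-lab contract running to 60 months. The 84-week spacing is a permitted extreme, not a typical interval.

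**Conclusion.** The point holds in a limited form. After year 1 the plan states no evaluation of device-related interim imaging and has no rule for counting an imaging event found and repaired between annual scans. Late endoleaks should still reach the data through case report forms, and late re-intervention and conversion through the primary endpoint. The exposed results are the 24 to 60 month summaries of migration, occlusion and new false-lumen perfusion, together with the evaluated image record for all four event types.

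Each omitted event is worth 5 percentage points with 20 patients. How many would be omitted cannot be derived from the documents. The conclusion rests on reading the one-year limit as having effect, and on some late failures being both imaged and treated between scheduled scans. The importance is minor: the secondary endpoints are descriptive, and neither the sample size nor the 30-day mortality test depends on them.

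**What to change.** Three edits are needed, the first in Section 3.3.4.6 and the other two there or in Section 3.3.5.3:

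1. Delete the five words that confine interim imaging to the first year. Device-related interim scans through 60 months would then be submitted and evaluated on the same footing as the scheduled late scans.
2. State that an endoleak, migration, occlusion or new false-lumen perfusion first seen on an interim scan counts as an event in the 24 to 60 month summaries, even if treated before the next scheduled scan.
3. Name the source, site or central read, that decides these events after month 12. Without this, the first edit leaves open how a late interim finding is used.

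The cost is a few extra submissions and reads of scans already taken. No scan, visit or patient is added, and alpha, power and patient management do not change.

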Pre-Enrollment Testing:	
 • Physical Exam • Vital Signs • Medical History • Pregnancy Test (if applicable) • Serum Creatinine • CTA of the chest/abdomen/pelvis, Echocardiogram.
Follow up Schedule:	
 • Discharge • 1 Month • 6 Months • 12 Months • Annually to 5 years
Centralized Image Analysis:	
Medical Data and Imaging System (M2S)
 
 • Coverage of Proximal entry tear • Aortic remodeling at 1 month, 6 month, 12 month, and annual visits up to 5 years as measured by: 
 - Change in TL size from baseline - Change in the FL Size from baseline - Change in total ascending aortic size from baseline FL Thrombosis - Continuing or new FL perfusion

Analytical Sets:	The primary endpoint analysis set will include all enrolled subjects who had at least one study scent graft implanted. The Intent-to-Treat (ITT) analysis set will include all enrolled subjects who had an intra-arterial access procedure with intent to receive the study device.
Study Monitor:	[name] Baylor Research Institute [name] [name]
Study Oversight:	A data safety monitoring committee will be used for oversight of the investigational site.

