3.3.5.3. Analysis of Endpoints

Data Analysis Sets

The primary endpoint analysis set will include all enrolled subjects who had at least one study stent graft implanted.

The Intent-to-Treat (ITT) analysis set will include all enrolled subjects who had an infra-arterial access procedure with intent to receive the study device. The primary endpoint will be reported for this analysis set as well.

Analysis of the Primary Endpoint

The primary endpoint will be analyzed using the exact binomial test method. The null hypothesis will be rejected if the upper limit of the one-sided 95% confidence interval on the 30 days mortality rate is less than 25%. The one-sided upper 95% confidence interval on the 30 days mortality rate will be calculated using the exact binomial test method.

The remainder of the primary endpoint will be presented and analyzed descriptively by reporting, for categorical variables, the number of known values and the percentage in each category, and for continuous variables, the number of known values, the mean, standard deviation (SD), median and the minimum and maximum number of subjects.

Analysis of the Secondary Observations

All secondary endpoints will be presented descriptively by reporting, for categorical variables the number of known values and the percentage in each category, and for continuous variables the number of known values, mean, standard deviation (SD), median, minimum and maximum of subjects meeting the endpoint.

Analysis of Baseline Variables

Baseline variables will be presented descriptively as described in the section above.

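### The CT section reports 24- to 60-month imaging from site data, while the synopsis puts the same late visits under central analysis; one reading source should be named for all visits

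*Combined protocol and SAP*

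**What the plan says.** Section 3.3.4.6 (CT/CTA Scan) sets out nine imaging time points: "Images at pre-procedure, pre-discharge, 1 month, 6 months, 12 months, 24 months, 36 months, 48 months and 60 months will be evaluated". It then assigns a use to the data in two steps. For the first year: "These data will be used for analysis of secondary observations at pre-discharge, 1 month, 6 months and 12 months". For the later visits: "Site data will be used for reporting purposes at 24 months, 36 months, 48 months and 60 months, and submitted for central review". The measures listed there are stent graft patency, true- and false-lumen diameter and volume, total aortic diameter, false-lumen thrombosis and perfusion, migration, and endoleak.

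The synopsis (3.1), in the row for Centralized Image Analysis by M2S, lists "Aortic remodeling at 1 month, 6 month, 12 month, and annual visits up to 5 years as measured by" a set of measures that includes "Change in TL size from baseline", with matching items for the false lumen and the total ascending aorta, plus false-lumen thrombosis and perfusion.

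Two other places bear on the point. Section 3.3.4.4 says that serial reconstruction with M2S or similar software "will allow for morphologic changes of the aorta and structural changes of the stent graft in the long-term follow-up". Section 3.4.2 says: "The imaging core lab will be used for patient safety review and measures", with no time limit.

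On analysis, 3.3.5.3 states: "All secondary endpoints will be presented descriptively by reporting, for categorical variables the number of known values and the percentage in each category", with summary statistics for continuous variables. It has no adjustment for reader and no rule for disagreement between readings.

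**The concern.** A change from baseline can be interpreted only if both ends are measured in the same way. If the baseline and first-year scans are read centrally and the scans from year 2 on are reported from site readings, time and reader change at the same visit. A step between 12 and 24 months could then come from the aorta, from the reader, or from both. With a purely descriptive analysis, nothing downstream separates them.

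For findings recorded as present or absent, chiefly endoleak and loss of patency, the problem takes another form. Nothing is subtracted, but a late rate found by one process is set beside an early rate found by another. Section 3.3.3 makes lesion exclusion and graft patency at annual visits through 5 years part of what the study sets out to determine, so the late imaging is not incidental.

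**Working it through.** The plan states no figure on this point, so there is none to reproduce. The check is a comparison of sections, a count, and an illustration on assumed values.

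**1. Which source applies, measure by measure, at 24 to 60 months**

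| Measure | Synopsis, central analysis | Section 3.3.4.6 | Consequence if 3.3.4.6 is followed |
|---|---|---|---|
| True-lumen, false-lumen, total aortic size | annual to 5 years, change from baseline | site data | conflict; reader change enters the late change |
| False-lumen thrombosis, perfusion | annual to 5 years | site data | conflict; different ascertainment |
| Migration, endoleak, patency | not listed | site data | the site-data sentence is the only stated rule; different ascertainment |

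The sentence on the first-year data in 3.3.4.6 does not name its reader. Central reading is inferred from the contrast with site data in the next sentence and from the synopsis.

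**2. Count of time points**

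Scheduled post-procedure CT: pre-discharge, 1, 6, 12, 24, 36, 48 and 60 months, which makes 8. Reported from site data: 24, 36, 48 and 60 months, which makes 4. The share is 4/8. Section 3.3.4.3 allows one CT set to serve both discharge and 1 month when the two coincide; for such a patient the share is 4/7.

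**3. How an offset would enter a size measure**

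Let the true size at visit t be T(t), and let site readings differ from central readings by a constant b. Ignoring random error:

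- Change from baseline at 12 months, both central: T(12) − T(0).
- Change from baseline at 24 months, site minus central: T(24) − T(0) + b.
- Step from 12 to 24 months: T(24) − T(12) + b.
- Step from 24 to 36 months, both site: T(36) − T(24); b cancels.

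So b passes in full into every comparison that crosses the 12/24-month boundary. It does not affect comparisons within the late visits, provided that b is constant.

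**4. Illustration on assumed values**

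The documents give neither b nor the SD of within-patient change. Assume no true change from 12 to 24 months and a normal approximation, with SE = SD/√n. The probability that a two-sided 95% interval for the mean change excludes zero is

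P = 1 − Φ(1.96 − b/SE) + Φ(−1.96 − b/SE).

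Example: n = 20 (planned enrollment), SD = 3 mm, b = 2 mm. SE = 3/√20 = 0.671, b/SE = 2.98, P = 0.846.

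| n | SD (mm) | b = 0 | b = 1 mm | b = 2 mm | b = 3 mm |
|---|---|---|---|---|---|
| 20 | 3 | 0.05 | 0.320 | 0.846 | 0.994 |
| 20 | 5 | 0.05 | 0.145 | 0.432 | 0.765 |
| 10 | 3 | 0.05 | 0.184 | 0.559 | 0.885 |
| 10 | 5 | 0.05 | 0.097 | 0.244 | 0.475 |

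The rows with n = 10 assume attrition. With a single source throughout, b = 0 and the probability is the nominal 0.05. The plan does not specify this interval; it serves only to show when an offset would be large relative to sampling error.

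**The case against.** The strongest reply is that a full switch of reader is not established. Section 3.3.4.6 never names a core lab, has images at all nine time points evaluated, and sends the late data for central review. The synopsis plans central analysis to year 5, 3.3.4.4 describes M2S or similar software for long-term follow-up, and 3.4.2 gives the core lab an open-ended role. On that reading, central values will exist at every visit. This stands as a limit: the mixing of reader and time is conditional on site values being the ones reported. It does not remove the conflict, because 3.3.4.6 says that site data are what will be reported, and no section says what the central review yields or which reading prevails.

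The reply is also right that this is a 20-patient feasibility study with descriptive secondary endpoints, and that the only hypothesis test concerns 30-day mortality. That limits the consequences. But where the analysis is descriptive, the reported value is the result, so its source matters.

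Three stronger readings are tempting and are not supported:

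- *The late readers are the unblinded implanting team.* Site data does not identify the reader, and 3.4.2 lists imaging cardiology and diagnostic radiology among the site's services. Nor do the documents say that core-lab readers are blinded.
- *All late-durability data are affected.* Late death, re-intervention and surgical conversion are primary endpoints, and echocardiogram and chest x-ray continue at years 2 to 5. None of these depends on who reads the CT.
- *Every imaging endpoint is a difference from a centrally read baseline.* Endoleak, patency and migration have no value before a graft is in place. The subtraction argument applies to the size measures only.

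**Conclusion.** The point holds as an unreconciled conflict over the source of the late CT readings, and it should be corrected. If 3.3.4.6 is followed as written, 4 of 8 scheduled post-procedure CT time points are reported from a different source than the first year. For true-lumen, false-lumen and total aortic size, any systematic difference between site and central reading would then appear in full as late change. For endoleak, migration and patency, late findings would not be ascertained in the same way as first-year findings.

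This rests on one inference, that the evaluated data to 12 months are central readings, and on one condition, that site values are what is reported later. A reader might take the table of probabilities as evidence that the late results will be biased. It is not: the offsets and SDs are assumed, and the documents contain nothing from which to estimate them. The 30-day mortality test is unaffected.

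**What to change.** Replace the site-data sentence in 3.3.4.6 with wording such as: *Core-lab readings are the analysis data at every scheduled CT/CTA visit from pre-procedure to 60 months. Site readings are listed separately, and discrepancies between site and core-lab readings are reported.* Extend the use for secondary observations to the 24- to 60-month visits in the same paragraph. Align the central-analysis row of the synopsis, and add migration, endoleak and patency to it so that the two lists match.

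The cost is small: waiting for and recording core-lab measurements on images that 3.3.4.6 already has submitted through 60 months. It would be somewhat higher if central review of the late data was not meant to produce measurements; the documents do not say, and the sponsor should confirm this.
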